The study will consist of **12 weeks of open label trial** with treatment of oral Glutathione in 24 subjects with ASD; the subjects will be recruited at the University of Chicago. Subjects will be seen every two weeks for the first month and then every four weeks for the remaining two months with one final visit at the end of the study for a total of 5 visits.

Study Location

This is a single-site trial in the United States, with a total of 24 subjects aged 4-17. The Principal

Page 6 of 17 IRB19-0017 Version 2; date: 4/11/19 Investigator for this study is:

[name]. Professor of Child and Adolescent Psychiatry University of Chicago [name]

All subjects will be seen in the Department of Child and Adolescent Psychiatry at the University of Chicago Medical Center at [name]. The offices are connected to the Department of Psychiatry and provide confidential interview rooms and facilities.

Investigational Agent

Glutathione (GSH) Reduced (Oral Capsules - Jarrow Brand)

- for patients 40kg or less: 500 mg by mouth twice a day for two weeks, then 1000 mg by mouth twice a day for ten weeks.
- for patients greater than 40 kg: 500 mg by mouth twice a day for two weeks, then 1000 mg by mouth twice a day for two weeks, then 1000 mg by mouth each morning and 2000 mg by mouth every afternoon for eight weeks.
- Dosages will be increased based on tolerability and the monitoring of any potential GI side effects as determined by the investigator.

Dosing Regimen for ≤40kg group (BID dosing throughout study)

Week 0 (Visit 1) – Week 2 (Visit 2): 1000mg/day (500mg po qam and 500mg po qpm)
Week 2 (V2) – Week 12 (V5): 2000mg/day (1000mg po qam and 1000mg po qpm)

Dosing Regimen for ≥40kg group (BID dosing throughout study)

 Week 0 (Visit 1) – Week 2 (Visit 2):
 1000mg/day (500mg po qam and 500mg po qpm)

 Week 2 (V2) – Week 4 (V3):
 2000mg/day (1000mg po qam and 1000mg po qpm)

 Week 4 (V3) – Week 12 (V5):
 3000mg/day (1000mg po qam and 2000mg po qpm)

Maximum Amount of Study Drug Needed

V1: 1000mg = 2 (500mg) pills x 14 days = 28 pills V2: 2000mg = 4 (500mg) pills x 14 days = 56 pills V3: 3000mg = 6 (500mg) pills x 28 days = 168 pills V4: 3000mg = 6 (500mg) pills x 28 days = 168 pills

V5: none dispensed (end of study) total per subject: 420 pills

TOTAL PILLS for 24 subjects = \sim 10,080pills maximum (based on recruiting patients \geq 40kg)

SUMMARY OF DATA COLLECTION AND STUDY PROCEDURES BY VISIT							

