Unanticipated (unexpected) problems/events, those that are not already described as potential risks in the consent form, or not part of an underlying disease, will be reported to the IRB within 10 business days. The same will be done for serious problems/events and, in the opinion of the investigator, are possibly, probably or definitely related to the research procedures. A follow-up report will also be submitted to the IRB with any documentation related to a previously submitted adverse event.

Procedure:

Twenty-four (24) subjects will be recruited to receive oral Glutathione reduced in this open-label trial. All parents of the subjects will be provided with informed consent forms and verbal assent from subjects ≥ 6 years of age will be obtained after an age appropriate version of the informed consent forms are read to them. The Child Psychiatry clinicians/nurses, patients and parents will be aware of the medication name and dosing schedules as indicated. The clinic nurse will obtain vitals at each visit. Glutathione will be the only study medication dispensed to subjects for this study. Subjects will be told to take the first dose of study medication after breakfast each day and the second dose in the evening after dinner. Subjects will be told to monitor and report any side effects experienced to the study staff at each visit or immediately if they wish (via one of the

Page 12 of 17 IRB19-0017 Version 2: date: 4/11/19 multiple telephone numbers for the study physicians and study staff given to them at each visit).

Psychotherapy of any form (including cognitive-behavioral therapy) will be reported to the PI during the study.

Subjects will be evaluated with the Aberrant Behavior Checklist (ABC), Social Responsiveness Scale (SRS) and CGI at screening and at each visit for the remainder of the study. Medication side effects will be evaluated at each study visit. A tablet count will be kept for each dose of medication taken to monitor adherence.

Dosing Regimen for Glutathione

The proposed dose range for Glutathione in this study will be 1000mg-3000mg/day based on the subject's weight. A previous observational study of children with Cystic Fibrosis showed that this population responded well and were able to absorb Glutathione with a daily dose of 65mg/kg (10).

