As Cystic Fibrosis is a condition that typically results in malabsorption of fats and other products, it is our thought that subjects with normal gastrointestinal (GI) systems may also absorb Glutathione effectively and at a slightly lower milligram starting dose, which is proposed to be ~32.5mg/kg. No adverse events were noted in the above mentioned study; however, to ensure tolerability in subjects with normal functioning GI systems, starting at a low dose and titrating up accordingly will be the most conservative and safe method.

Timeline:

Recruitment for the proposed study will begin as soon as the study drug is available and IRB approval is confirmed. It is anticipated that all subjects would be entered into the study within approximately 6 months, and that the study would be completed within 12 months of initiation.

Ethical Considerations:

This study will be conducted according to US and international standards of Good Clinical Practice (FDA regulations 21 CFR 312 for IND studies and FDA guidance E6) for all studies. Applicable government regulations and University of Chicago research policies and procedures will also be followed.

This protocol and any amendments will be submitted to the University of Chicago Institutional Review Board (IRB) for formal approval to conduct the study. The decision of the IRB concerning the conduct of the study will be made in writing to the investigator.

Parents of all subjects for this study will be provided a consent form describing this study and providing sufficient information for parents to make an informed decision about their participation in this study. This consent form will be submitted with the protocol for review and approval by the IRB. The formal consent of parents of subjects, using the IRB- approved consent form, will be obtained before that subject is submitted to any study procedure. This consent form must be signed by the parents of subjects or legally acceptable surrogate, and the investigator-designated research professional obtaining the consent.

Data Handling and Record Keeping

Page 13 of 17 IRB19-0017 Version 2; date: 4/11/19 All subject data will be maintained by the study personnel under the supervision of the principal investigator. All subjects will be seen in the Department of Child and Adolescent Psychiatry at the University of Chicago Medical Center at [name]. Patient folders will be kept in a locked cabinet only accessible to research staff.

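### The per-kg dose rationale does not match the flat doses: planned maintenance exceeds 65 mg/kg/day, the only exposure cited with a tolerability statement, below 30.8 kg and from about 40 to 46.2 kg

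*Combined protocol and SAP*

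**What the plan says.** The section Dosing Regimen for Glutathione gives the reasoning per kilogram. It cites one observational study of children with cystic fibrosis, in which "this population responded well and were able to absorb Glutathione with a daily dose of 65mg/kg (10", and adds that "No adverse events were noted in the above mentioned study". It expects children with normal gut function to absorb glutathione at a "slightly lower milligram starting dose, which is proposed to be ~32.5mg/kg", and it adds a low start and upward titration to protect tolerability. It summarises the plan this way: "The proposed dose range for Glutathione in this study will be 1000mg-3000mg/day based on the subject's weight".

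The section Investigational Agent, under Methods, gives the doses as flat amounts in two weight bands. Everyone starts at 500 mg twice daily for two weeks.

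- At 40 kg or less: "then 1000 mg by mouth twice a day for ten weeks", which is 2000 mg/day.
- Above 40 kg, after two weeks at 2000 mg/day: "then 1000 mg by mouth each morning and 2000 mg by mouth every afternoon for eight weeks", which is 3000 mg/day.

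One sentence makes these steps conditional: "Dosages will be increased based on tolerability and the monitoring of any potential GI side effects as determined by the investigator".

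The bullets split the bands at 40 kg or less and greater than 40 kg. The schedule printed below them heads its second block "Dosing Regimen for ≥40kg group (BID dosing throughout study", and the pill total also uses 40 kg or more for the heavier group. The inclusion criteria set an age range of 4 to 17 and no minimum weight.

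**The concern.** A flat dose gives the highest exposure per kilogram to the lightest child in each band. The rationale is a per-kg figure, so it supports the flat doses only at weights where the two coincide or the flat dose falls below the figure. The protocol never converts one into the other, and an investigator or ethics board reading the rationale cannot tell which children it covers.

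Tolerability is one of the three stated aims and change in blood glutathione is the primary outcome. Both depend on the exposure each child receives, yet the Data Analysis section plans no summary by mg/kg/day. Without one, the study's guidance on dose for a later trial is harder to read.

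**Working it through.** **Inputs.** Cited exposure 65 mg/kg/day and proposed start about 32.5 mg/kg (Dosing Regimen for Glutathione). Flat doses 1000, 2000 and 3000 mg/day (Investigational Agent). The documents give no body weights, so every individual weight below is an assumption. The threshold weights need no such assumption.

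**Reproducing the plan's own figures.** Pills per subject in the heavier band: 2×14 + 4×14 + 6×28 + 6×28 = 28 + 56 + 168 + 168 = 420. For 24 subjects: 420 × 24 = 10,080. Both match the protocol, which confirms the 1000/2000/3000 mg/day schedule. The proposed start is 65/2 = 32.5 mg/kg, half the cited exposure.

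**Threshold weights.** Weight at which a flat dose equals a per-kg figure = daily dose ÷ mg/kg.

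- 2000/65 = 30.77 kg. Lower-band maintenance exceeds the cited exposure below this weight.
- 3000/65 = 46.15 kg. Upper-band maintenance exceeds it from the bottom of that band, about 40 kg, to this weight.
- 1000/32.5 = 30.77 kg. The flat start equals the proposed per-kg start only here.
- 1000/65 = 15.38 kg. Below this weight the starting dose alone is above the cited exposure.

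**Exposure by weight.** mg/kg/day = daily dose ÷ weight.

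| Weight (kg) | Start, 1000 mg/day | Maintenance | Maintenance ÷ 65 |
|---|---|---|---|
| 15 | 66.7 | 2000/15 = 133.3 | 2.05 |
| 16 | 62.5 | 2000/16 = 125.0 | 1.92 |
| 20 | 50.0 | 2000/20 = 100.0 | 1.54 |
| 25 | 40.0 | 2000/25 = 80.0 | 1.23 |
| 30 | 33.3 | 2000/30 = 66.7 | 1.03 |
| 35 | 28.6 | 2000/35 = 57.1 | 0.88 |
| 40 (lower band) | 25.0 | 2000/40 = 50.0 | 0.77 |
| 40 (upper band) | 25.0 | 3000/40 = 75.0 | 1.15 |
| 45 | 22.2 | 3000/45 = 66.7 | 1.03 |
| 50 | 20.0 | 3000/50 = 60.0 | 0.92 |
| 60 | 16.7 | 3000/60 = 50.0 | 0.77 |

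**The 40 kg boundary.** Under the bullets, a child of exactly 40 kg is in the lower band only. Under the schedule headings the same child is in both. The planned maintenance exposure is then 50 or 75 mg/kg/day, a ratio of 75/50 = 1.5.

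**Other support in the text.** No other section gives a per-kg exposure, a mg/kg ceiling, or the exposures the flat doses produce. The reference list includes a glutathione supplementation trial in autism, but the Background cites it only for glutathione's levels, role and pathway, with no dose or tolerability figure.

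**The case against.** The strongest reply is that the flat doses are conditional targets. The investigator escalates only if the child tolerates the current dose, so some children may never reach 2000 or 3000 mg/day. This stands, and it rules out saying that every child under 30.8 kg will receive more than 65 mg/kg/day. It does not close the gap. Titration detects reactions after exposure and does not extend the cited support to higher exposures. In the lightest children the start is also not low per kilogram.

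Second, the protocol cites 65 mg/kg/day for response and absorption and never calls it a ceiling. Its claim to be conservative and safe is attached to the low start and titration, not to the precedent. Both points are correct. A reader might infer that the regimen breaches a safety limit or is unsafe in small children; the documents set no such limit and give no evidence of harm above 65.

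Third, several further inferences are tempting but unsupported:

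- That parents are being misinformed. The consent pages are not available, so their content cannot be checked.
- That weight is never measured. The procedures table omits it, but the table also omits the screening physical examination, concomitant medications and the tablet count, all of which are planned in the text. What can be said is that no section states when weight is taken.
- That exposure varies more than threefold. This holds for assumed weights of 16 to 80 kg (125/37.5 = 3.3), but over an assumed 20 to 60 kg the range is 50 to 100 mg/kg/day, or twofold.
- That pooling will hide gastrointestinal effects in the smallest children. Side effects are assessed at each visit, no summary by band is planned, and nothing in the documents says these effects depend on mg/kg.

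**Conclusion.** The narrowed point holds. The per-kg rationale and the flat regimen disagree in three places:

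- maintenance targets exceed the only exposure cited with a tolerability statement below 30.8 kg and from about 40 to 46.2 kg;
- the stated starting dose per kilogram agrees with the flat start at a single weight;
- the two weight bands overlap at exactly 40 kg.

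The thresholds follow directly from the protocol's own figures. The size of the excess in the youngest children rests on an assumed weight of 15 to 20 kg. In the upper band it is at most about 1.15 times, at the 40 kg edge. The conclusion concerns what the cited evidence covers; it makes no judgement on whether any dose is right or wrong. The correction is cheap and bears on safety, so it should be made.

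**What to change.** The sponsor should reconcile Dosing Regimen for Glutathione with Investigational Agent, covering the starting dose, the maintenance targets and the 40 kg boundary, and should state the mg/kg/day range the regimen produces. It should then either cite support for exposures above 65 mg/kg/day or state that the precedent does not cover children below about 31 kg or from about 40 to 46 kg. If the consent form cites the precedent, the same statement belongs there. No dose is proposed here.

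Weight should be recorded with the vitals at baseline and at week 4, where the two regimens diverge. The visit should be named by week, because Methods counts five visits and the procedures table shows screening plus six. Side effects and glutathione change should be tabulated by actual mg/kg/day as well as pooled.

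The cost is a slightly less favourable rationale, a weight added to scheduled vitals, and one descriptive table. With 24 children that table can describe a pattern but cannot establish a dose-response relation.

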
Diagnostic Criteria for Autism Spectrum Disorder (1)

The following diagnostic criteria for ASD will be utilized. Criteria are defined by the Diagnostic and Statistical Manual for Mental Disorders (DSM-5) for a diagnosis of Autism Spectrum Disorder (1):

- A. Persistent deficits in social communication and social interaction across multiple contexts, as manifested by the following, currently or by history (examples are illustrative, not exhaustive, see text):
- 1. Deficits in social-emotional reciprocity, ranging, for example, from abnormal social approach and failure of normal back-and-forth conversation; to reduced sharing of interests, emotions, or affect; to failure to initiate or respond to social interactions.
- 2. Deficits in nonverbal communicative behaviors used for social interaction, ranging, for example, from poorly integrated verbal and nonverbal communication; to abnormalities in eye contact and body language or deficits in understanding and use of gestures; to a total lack of facial expressions and nonverbal communication.
- 3. Deficits in developing, maintaining, and understanding relationships, ranging, for example, from difficulties adjusting behavior to suit various social contexts; to difficulties in sharing imaginative play or in making friends; to absence of interest in peers.
- Specify current severity: Severity is based on social communication impairments and restricted repetitive patterns of behavior.
- B. Restricted, repetitive patterns of behavior, interests, or activities, as manifested by at least two of the following, currently or by history (examples are illustrative, not exhaustive; see text):
- 1. Stereotyped or repetitive motor movements, use of objects, or speech (e.g., simple motor stereotypies, lining up toys or flipping objects, echolalia, idiosyncratic phrases).
- 2. Insistence on sameness, inflexible adherence to routines, or ritualized patterns or verbal nonverbal behavior (e.g., extreme distress at small changes, difficulties with transitions, rigid thinking patterns, greeting rituals, need to take same route or eat food every day).
- 3. Highly restricted, fixated interests that are abnormal in intensity or focus (e.g., strong attachment to or preoccupation with unusual objects, excessively circumscribed or perseverative interest).
- 4. Hyper- or hyporeactivity to sensory input or unusual interests in sensory aspects of the environment (e.g., apparent indifference to pain/temperature, adverse response to specific sounds or textures, excessive smelling or touching of objects, visual fascination with lights or movement). *Specify* current severity: Severity is based on social communication impairments and restricted, repetitive patterns of behavior.
- C. Symptoms must be present in the early developmental period (but may not become fully manifest until social demands exceed limited capacities or may be masked by learned strategies in later life).
- D. Symptoms cause clinically significant impairment in social, occupational, or other important areas of current functioning.
- E. These disturbances are not better explained by intellectual disability (intellectual developmental disorder) or global developmental delay. Intellectual disability and autism spectrum disorder frequently co-occur; to make comorbid diagnoses of autism spectrum disorder

Page 16 of 17 IRB19-0017

Version 2; date: 4/11/19

and intellectual disability, social communication should be below that expected for general developmental level.

Note: Individuals with a well-established DSM-IV diagnosis of autistic disorder, Asperger's disorder, or pervasive developmental disorder not otherwise specified should be given the diagnosis of autism spectrum disorder. Individuals who have marked deficits in social communication, but whose symptoms do not otherwise meet criteria for autism spectrum disorder, should be evaluated for social (pragmatic) communication disorder.

Specify if:

- With or without accompanying intellectual impairment
- With or without accompanying language impairment
- Associated with a known medical or genetic condition or environmental factor
- Associated with another neurodevelopmental, mental, or behavioral disorder
- With catatonia
